## Check All That Apply

- Grant application pending
- (HHS) Dept. of Health & Human Services
  - (NIH) National Institutes of Health
  - (CDC) Centers for Disease Control & Prevention
  - (HRSA) Health Resources and Services Administration
  - (SAMHSA) Substance Abuse and Mental Health Services Administration
- (DoJ) Department of Justice or Bureau of Prisons
- (DoE) Department of Energy
- (EPA) Environmental Protection Agency
- Federal Agencies Other Than Those Listed Here
- Industry (Other than Pharmaceutical Companies)
- Internal Grant Program w/ proposal
- Internal Grant Program w/o proposal
- National Science Foundation
- Other Institutions of Higher Education
- Pharmaceutical Company
- Private Foundation/Association
- U.S. Department of Education
- State

Other:

Click applicable listing(s) for additional requirements and information:

- [\(HHS\) Dept. of Health & Human Services](#)
- [\(NIH\) National Institutes of Health](#)
- [\(CDC\) Centers for Disease Control & Prevention](#)
- [\(HRSA\) Health Resources & Services Administration](#)
- [\(SAMHSA\) Substance Abuse & Mental Health Services Administration](#)
- Industry (Other than Pharmaceutical Companies) [[IRB Fee Info](#)]
- [National Science Foundation](#)
- [\(DoEd\) U.S. Department of Education](#)
- [\(DoJ\) Department of Justice or Bureau of Prisons](#)
- [\(DoE\) Department of Energy Summary and Department of Energy Identifiable Information Compliance Checklist](#)
- [\(EPA\) Environmental Protection Agency](#)

Specify the funding source and/or cooperating organization(s) (e.g., National Cancer Institute, Ford Foundation, Eli Lilly & Company, South Western Oncology Group, Bureau of Prisons, etc.):

Markey Cancer Center and Lexicon Pharmaceuticals, Inc.

## Add Related Grants

If applicable, please search for and select the OSPA Account number or Electronic Internal Approval Form (eIAF) # (notif #) associated with this IRB application using the "Add Related Grants" button.  
If required by your funding agency, upload your grant using the "Grant/Contract Attachments" button.

[Add Related Grants](#)

[Grant/Contract Attachments](#)

The research involves use of Department of Defense (DoD) funding, military personnel, DoD facilities, or other DoD resources.  
(See [DoD SOP](#) and [DoD Summary](#) for details)

Yes  No

Using the “attachments” button (below), attach applicable materials addressing the specific processes described in the DoD SOP.

[DOD SOP Attachments](#)

Additional Certification: (If your project is federally funded, your funding agency may request an Assurance/ Certification/Declaration of Exemption form.) Check the following if needed:

Protection of Human Subjects Assurance/Certification/Declaration of Exemption (Formerly Optional Form – 310)

[Assurance/Certification Attachments](#)

## 9. STATISTICAL CONSIDERATIONS

### 9.1 Study Design/Endpoints

This is an open label, randomized, parallel arm, Phase II trial of two dose levels of Telotristat (250 mg TID and 500 mg TID) in combination with Lutetium Lu 177 Dotatate (Lutathera). The primary endpoint of the study is 20-month PFS. The study is designed to test a non-inferiority hypothesis for one proportion (proportion of patients had 20-month progression-free) for each arm separately. No interim analysis will be performed. All patients will be followed up to 36 months after the study enrollment. An intent-to-treat analysis will be performed and patients who drop-out prior to 20 months of follow-up will be deemed non-evaluable for the primary objective and excluded from primary objective analysis. PFS distribution and median PFS will be estimated using Kaplan-Meier method based on 36 months follow-up data.

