## Study Design/Endpoints

This is an open label, randomized, parallel arm, Phase II trial of two dose levels of Telotristat (250 mg TID and 500 mg TID) in combination with Lutetium Lu 177 Dotataate (Lutathera). The primary endpoint of the study is 20-month PFS. The study is designed to test a non-inferiority hypothesis for one proportion (proportion of patients had 20-month progression-free) for each arm separately. No interim analysis will be performed. All patients will be followed up to 36 months after the study enrollment. An intent-to-treat analysis will be performed and patients who drop-out prior to 20 months of follow-up will be deemed non-evaluable for the primary objective and excluded from primary objective analysis. PFS distribution and median PFS will be estimated using Kaplan-Meier method based

on 36 months follow-up data.

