### 9.2 Sample Size/Accrual Rate

A sample of 33 patients per arm will provide 80% power to test a non-inferiority difference of 5% for the combination based on a one-sided test with 5% significance level. Based on the NETTER trial [7], we will assume that PFS rate at 20 months is equal to 65%. We will further assume a small non-inferiority margin of 5% and that the PFS at 20 months with the PRRT (Lutathera)+Telotristat combination is equal to 80%. The assumption in hypothesized effect size of the combination is based on the width of the 95% confidence interval presented in the NETTER trial results. If at least 25 out of 33 patients in each arm progression-free at 20 months, we will conclude that PFS rate at 20 months for the combination (either arm) is non-inferior. To account for a potential 5% drop-out/non-evaluable rate, we will enroll 35 patients per arm. We expect to enroll 2-3 patients per month. Thus, a total of 70 patients requires an accrual duration approximate of 30 months (2.5 years) and study duration approximate of 66 (5.5 years) months (30 months accrual plus 36 months follow-up)

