### 9.3 Analysis of Primary Endpoint

Hypothesis testing based on non-inferiority of PFS rate at 20 months will be performed for each arm using an exact test for one proportion. Furthermore, PFS will be estimated using the Kaplan Meier method and estimates at 20 months, other specific time points and 95% confidence interval will be calculated. Survival analysis models such as Cox regression will also be considered.

An intent-to-treat analysis will be initially performed wherein all patients who received at least one dose of the treatment regimen is included in the analysis. For the primary endpoint of PFS at 20 months, patients who drop-out and are not evaluated for the 20 month time point will be considered non-evaluable. Subjects will be followed for up to 36 months in order to capture significant events and median PFS (secondary endpoint) estimates.

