### **9.7.2 Evaluation of Response as Secondary Endpoint**

All patients included in the study must be assessed for response to treatment, even if there are major protocol treatment deviations or if they are ineligible. Each patient will be assigned one of the following eight categories:

- 1) complete response,
- 2) partial response,
- 3) stable disease,
- 4) progressive disease,
- 5) early death from malignant disease,
- 6) early death from toxicity,
- 7) early death because of other cause, or
- 9) unknown (not assessable, insufficient data)

All of the patients who met the eligibility criteria (with the possible exception of those who received no study medication) should be included in the main analysis of the response rate. Patients in response categories 4-9 should be considered to have a treatment failure (disease progression). Thus, an incorrect treatment schedule or drug administration does not result in exclusion from the analysis of the response rate. Precise definitions for categories 4-9 will be protocol specific but primarily follow RECIST v1.1.

All conclusions should be based on all eligible patients. Sub-analyses may then be performed on the basis of a subset of patients, excluding those for whom major protocol deviations have been identified (*e.g.*, early death due to other reasons, early discontinuation of treatment, major protocol violations, *etc.*). However, these sub-analyses may not serve as the basis for drawing conclusions concerning treatment efficacy, and the reasons for excluding patients from the analysis should be clearly reported. The 95% confidence intervals should also be provided.

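### Sections 9.1 and 9.3 disagree on who enters the primary 20-month PFS test, and 9.1 read literally removes patients who progressed and then left

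*Combined protocol and SAP*

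**What the plan says.** The deciding analysis is in 9.3: "Hypothesis testing based on non-inferiority of PFS rate at 20 months will be performed for each arm using an exact test for one proportion". Section 9.2 sets the null at 65% minus a 5% margin, assumes 80% with the combination, and gives the success rule: "If at least 25 out of 33 patients in each arm progression-free at 20 months". It allows for losses: "To account for a potential 5% drop-out/non-evaluable rate, we will enroll 35 patients per arm".

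Three statements define who is counted:

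- Section 9.1: "An intent-to-treat analysis will be performed and patients who drop-out prior to 20 months of follow-up will be deemed non-evaluable". The sentence goes on to exclude them from the primary analysis. The same wording appears under Study Design/Endpoints in the Research Description of the IRB application: "patients who drop-out prior to 20 months of follow-up will be deemed non-evaluable for the primary objective and excluded from primary objective analysis".
- Section 9.3, on intent-to-treat: "all patients who received at least one dose of the treatment regimen is included in the analysis".
- Section 9.3, on the primary endpoint: "patients who drop-out and are not evaluated for the 20 month time point will be considered non-evaluable".

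Section 9.3 also plans a Kaplan-Meier estimate at 20 months, in addition to the exact test. For response rate only, 9.7.2 counts patients of unknown status as treatment failures.

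**The concern.** An analysis cannot be intent-to-treat in the sense of 9.3 (everyone dosed) and also leave out dosed patients who drop out. Nor are the two exclusions the same. Section 9.1 turns on when the patient left; 9.3 also requires that the 20-month evaluation is missing. Two analysts following the plan could reach different denominators.

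The patient who matters most is the one with documented progression who then leaves before month 20. That patient's 20-month status is known and is a failure. Section 9.1 read literally removes the patient. Section 9.3 does not settle it either, because someone who left after progressing may have no 20-month evaluation. Removing known failures can only raise the tested rate, in favour of declaring non-inferiority.

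Drop-outs whose status is truly unknown are a separate and weaker issue. Leaving them out shifts the tested rate only if their outcomes differ from those of the patients who stay.

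**Working it through.** **Inputs from the documents.** Null rate 0.65 − 0.05 = 0.60, assumed true rate 0.80, one-sided 5% level, 33 evaluable and 35 enrolled per arm, 5% drop-out (all 9.2); exact one-proportion test (9.3). **Assumed, because the documents give no value:** the share *f* of drop-outs who would have progressed by month 20, the share *s* of progressors who are deleted, and a 10% drop-out rate used for comparison.

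**1. The plan's own figures.** P(X≥25 | 33, 0.60) = 0.0444 and P(X≥24 | 33, 0.60) = 0.0923, so 25 is the smallest valid cut-off. P(X≥25 | 33, 0.80) = 0.800. 33/0.95 = 34.7, so 35 enrolled. All reproduce.

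**2. One patient under literal 9.1.** Suppose 35 are dosed and 26 are progression-free.
- All counted: P(X≥26 | 35, 0.60) = 0.058. The cut-off is 27 (P = 0.026), so the arm fails.
- One of the nine progressors left before month 20 and is removed: P(X≥26 | 34, 0.60) = 0.034. The cut-off is 26, so the arm passes.

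**3. Literal 9.1 in general.** At a true rate of 0.60, expected progressors are 35 × 0.40 = 14. If a share *s* is deleted, each patient is removed with probability 0.40*s* and the tested rate is 0.60/(1 − 0.40*s*). The level is averaged over the binomial number removed, using the exact cut-off at each remaining number.

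| *s* | tested rate | level |
|---|---|---|
| 5% | 0.612 | 4.2% |
| 10% | 0.625 | 6.2% |
| 12.5% | 0.632 | 7.2% |

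The level passes 5% at *s* ≈ 7%, and 0.07 × 14 ≈ 1 patient.

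**4. Drop-outs of unknown status.** With drop-out rate *d*, the tested rate is (0.60 − *d*(1 − *f*))/(1 − *d*), averaged in the same way.

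| *f* | level, *d* = 5% | level, *d* = 10% (assumed) |
|---|---|---|
| 40% (unrelated to outcome) | 3.4% | 3.4% |
| 70% | 5.0% | 7.3% |
| 80% | 5.7% | 9.2% |
| 100% | 7.2% | 14.2% |

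The 5% level is passed at *f* ≈ 69% and 55% respectively. These are averages. Given exactly 33 evaluable, where the exact level already sits at 4.4%, it is passed at *f* ≈ 48% and reaches 10.0% at 100%. Exactly 33 occurs in 27% of trials at 5% drop-out.

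The 7.2% here and the 7.2% in step 3 are one calculation, since 0.40 × 0.125 = 0.05.

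In the other direction, at a true 80% and 5% drop-out, averaged power is 76.0% if leaving is unrelated to outcome. It is 70.9% if no drop-out would have progressed.

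**5. Operating figures for the fix.**
- *Non-evaluable counted as failures, 27 of 35.* The level is 2.6%. With 5% unrelated drop-out the success rate is 0.80 × 0.95 = 0.76, and P(X≥27 | 35, 0.76) = 0.530.
- *Progressors kept, other drop-outs excluded.* Assume independent exponential drop-out of 5% by month 20, with hazards over that period g = −ln 0.95 and h = −ln(true rate). The excluded share is g/(g+h) × (1 − e^−(g+h)). At 0.60 this is 3.9%, giving a tested rate of 0.57/0.961 = 0.593 and a level of 2.8%. At 0.80 it is 4.5%, giving 0.76/0.955 = 0.796 and power of 74.1%.

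**The case against.** The best defence is that 9.1 is a design summary and 9.3 the operative section, so the two are summary and detail. Progression is the endpoint event, all patients are to be followed for up to 36 months, and a sensible analyst would score a documented progressor as a failure. The PFS definition may also sit in protocol sections that are not in the supplied file, which begins its statistical text at section 9.

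That makes the harmful reading probably unintended, but it does not remove it. The exclusion in 9.1 is explicit, is repeated in the IRB application, and differs from 9.3. Nothing in the available text says which prevails. A definition of PFS elsewhere would not by itself cancel a stated exclusion from the primary analysis.

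Other parts of the defence stand. Evaluable-set analysis is an acceptable choice for a phase II trial. Section 9.7.2 governs response, not PFS; it shows only that the plan already has a failure convention for unknown status. A reader might also infer that 25 is a fixed count whatever the evaluable number. The documents do not support that: 9.2 gives 25 only for 33, and the exact one-sided 5% test already implies 25 of 32, 26 of 34 and 27 of 35.

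**Conclusion.** The concern holds in limited form. The description of the primary analysis set is contradictory, and the rule in 9.1, followed as written, can turn a failing arm into a passing one by deleting a single known failure. This should be fixed before the data are analysed.

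A reader might go further and infer that excluding drop-outs breaks the 5% level in this design generally. The documents do not support that. At the only drop-out rate they give, the averaged level stays at about 5% or below unless roughly 69% of drop-outs would have progressed, against 40% of all patients under the null. Nor should the literal-9.1 figures be added to the drop-out figures as a second effect, because they rest on the same arithmetic.

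The 25-of-33 rule, its 4.4% level and its 80% power are correct for 33 evaluable patients. All magnitudes assume 35 per arm as in 9.2. The Project Information section lists a maximum of 12 subjects; that is a separate matter, but these figures would not apply at that size. The shares *f* and *s* and the 10% drop-out rate are assumptions.

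**What to change.** In 9.1, 9.3 and the matching IRB application text:

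1. State that any documented progression or death before 20 months counts as not progression-free, even if the patient later leaves.
2. Use one definition of non-evaluable: dosed, no documented progression or death, and no 20-month assessment.
3. Call the exact test the evaluable-set analysis, not intent-to-treat.
4. Report, as a sensitivity analysis and not the decision rule, the exact test in all dosed patients with non-evaluable patients counted as not progression-free (27 of 35 if 35 are dosed). Show it beside the planned Kaplan-Meier 20-month estimate, which stays descriptive with no pass/fail trigger and does not itself protect against informative drop-out.

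Listing the cut-offs for other evaluable numbers is an optional clarification. The primary test, the 25-of-33 rule and the sample size are unchanged.

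The cost is a few sentences and one extra analysis, with no new patients, visits or data. There are two downsides. The sensitivity test is conservative: at a true 80% with 5% unrelated drop-out it passes in 53.0% of trials against 74.1% for the primary test. Any trial that passes it also passes the primary test, so about 21% of trials would pass the primary test but not this one without any bias. Keeping progressors while excluding other drop-outs also makes the primary test slightly conservative when leaving is unrelated to prognosis: level 2.8% against 3.4%, power 74.1% against 76.0%.

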### 9.2 Sample Size/Accrual Rate

A sample of 33 patients per arm will provide 80% power to test a non-inferiority difference of 5% for the combination based on a one-sided test with 5% significance level. Based on the NETTER trial [7], we will assume that PFS rate at 20 months is equal to 65%. We will further assume a small non-inferiority margin of 5% and that the PFS at 20 months with the PRRT (Lutathera)+Telotristat combination is equal to 80%. The assumption in hypothesized effect size of the combination is based on the width of the 95% confidence interval presented in the NETTER trial results. If at least 25 out of 33 patients in each arm progression-free at 20 months, we will conclude that PFS rate at 20 months for the combination (either arm) is non-inferior. To account for a potential 5% drop-out/non-evaluable rate, we will enroll 35 patients per arm. We expect to enroll 2-3 patients per month. Thus, a total of 70 patients requires an accrual duration approximate of 30 months (2.5 years) and study duration approximate of 66 (5.5 years) months (30 months accrual plus 36 months follow-up)

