#### Sample Size/Accrual Rate

A sample of 33 patients per arm will provide 80% power to test a non-inferiority difference of 5% for the combination based on a one-sided test with 5% significance level. Based on the NETTER trial [7], we will assume that PFS rate at 20 months is equal to 65%. We will further assume a small non-inferiority margin of 5% and that the PFS at 20 months with the PRRT (Lutathera)+Telotristat combination is equal to 80%. The assumption in hypothesized effect size of the combination is based on the width of the 95% confidence interval presented in the NETTER trial results. If at least 25 out of 33 patients in each arm progression-free at 20 months, we will conclude that PFS rate at 20 months for the combination (either arm) is non-inferior. To account for a potential 5% drop-out/non-evaluable rate, we will enroll 35 patients per arm. We expect to enroll 2-3 patients per month. Thus, a total of 70 patients requires an accrual duration approximate of 30 months (2.5 years) and study duration approximate of 66 (5.5 years) months (30 months accrual plus 36 months follow-up).

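### Does the 25-of-33 success sentence leave open whether the arms are judged separately, and which rule applies when the evaluable number is not 33?

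*Combined protocol and SAP*

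**What the plan says.** Section 9.2 (Sample Size/Accrual Rate) puts the success criterion in one sentence. Its condition opens "If at least 25 out of 33 patients in each arm progression-free at 20 months, we will conclude that PFS rate at 20 months"; its closing words, which state the claim, are "for the combination (either arm) is non-inferior". The Sample Size/Accrual Rate text of the research description repeats it ("If at least 25 out of 33 patients in each arm progression-free at 20 months").

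The design claim earlier in 9.2 is per arm: "A sample of 33 patients per arm will provide 80% power to test a non-inferiority difference of 5% for the combination", one-sided at 5%, with an assumed historical 20-month rate of 65%, a margin of 5 points and a hoped-for rate of 80%. On enrolment, 9.2 says "To account for a potential 5% drop-out/non-evaluable rate, we will enroll 35 patients per arm".

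Two neighbouring sections define the test. Section 9.1: "The study is designed to test a non-inferiority hypothesis for one proportion (proportion of patients had 20-month progression-free) for each arm separately". Section 9.3: the non-inferiority test "will be performed for each arm using an exact test for one proportion". Objective 1.1.1 is likewise framed arm by arm. Section 9.1 adds that patients who drop out before 20 months "will be deemed non-evaluable for the primary objective and excluded from primary objective analysis", so the denominator of the primary analysis is not fixed in advance.

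**The concern.** There are two worries.

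First, the condition in 9.2 refers to each arm, but the conclusion is drawn once, for the combination, with either arm in brackets. That can be read as a both-arms rule or as an either-arm rule. A result of 24/33 in one arm and 27/33 in the other would be a success for one arm only if the arms are judged separately, a failure if both must pass, and a success for the combination if one is enough. Power and false-success rates differ accordingly.

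Second, 9.2 states a count and 9.3 names a test. The plan's own drop-out rule lets the evaluable number differ from 33, and no sentence says that the test takes precedence. If 25 were kept as a fixed count, an arm with 25 of 34 would meet the count yet have an exact p-value of 0.073. In an open-label trial, leaving such a choice until the results are known would be unwelcome.

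**Working it through.** **Inputs.** All come from 9.2: historical rate 65%, margin 5 points, alternative 80%, one-sided level 5%, 33 evaluable per arm, cut-off 25, non-evaluable rate 5%, 35 enrolled per arm. The null rate is not printed as a number; it follows as 65% − 5% = 60%.

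**Step 1: reproduce the stated design.** With X the number progression-free among n evaluable patients, size = P(X ≥ r | n, 0.60) and power = P(X ≥ r | n, 0.80).

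- n = 33, r = 25: size 0.0444, power 0.8000.
- n = 33, r = 24: size 0.0923, above 5%.

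So 25 is the smallest valid count at 33, and the 80% and 5% figures are per-arm figures. Enrolment: 33 / 0.95 = 34.7, rounded up to 35.

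**Step 2: compare the three readings at n = 33,** treating the arms as independent.

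| Reading | Size (both true rates 60%) | Power (both true rates 80%) |
|---|---|---|
| Each arm separately | 0.0444 per arm | 0.800 per arm |
| Both arms required | 0.0444² = 0.002 | 0.800² = 0.640 |
| Either arm suffices | 1 − (1 − 0.0444)² = 0.087 | 1 − (1 − 0.800)² = 0.960 |

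Only the first row matches the stated power and level, and it is the procedure that 9.1 and 9.3 describe.

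The 8.7% is not specific to a misreading. Two separate tests, each at an unadjusted 5% level, also leave an 8.7% chance that at least one arm passes falsely when both true rates are 60%. Rewording the sentence would not alter that.

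**Step 3: let the evaluable number vary.** Compare the exact-test cut-off with 25/33 applied as a proportion and rounded up.

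| Evaluable n | Exact cut-off (size, power) | 25/33 × n, rounded up | Size if a bare 25 is used |
|---|---|---|---|
| 30 | 23 (0.0435, 0.761) | 22.7 → 23 | 0.006 |
| 31 | 24 (0.0330, 0.730) | 23.5 → 24 | 0.013 |
| 32 | 25 (0.0248, 0.698) | 24.2 → 25 | 0.025 |
| 33 | 25 (0.0444, 0.800) | 25.0 → 25 | 0.044 |
| 34 | 26 (0.0341, 0.773) | 25.8 → 26 | 0.073 |
| 35 | 27 (0.0260, 0.745) | 26.5 → 27 | 0.112 |

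The second and third columns agree on every row. The first disagreement below 30 is at n = 29, where the proportion gives 22 (size 0.057) and the exact test needs 23.

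**Step 4: how often would the rules disagree?** Assume the evaluable number is binomial, 35 patients each with the stated non-evaluable rate. At 5%, the evaluable number falls between 30 and 35 with probability 0.993. Probability that a rule and the exact test give different answers for an arm, at a true rate of 80%:

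| Non-evaluable rate | 25/33 as a proportion | Bare count of 25 |
|---|---|---|
| 0% | 0 | 18.0% |
| 2% | below 0.001% | 12.6% |
| 5% (the plan's figure) | 0.09% | 8.2% |
| 10% | 1.2% | 15.0% |
| 15% | 3.5% | 30.3% |

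The last column applies only if the numerator is used without its denominator.

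**The case for a change.** The strongest case for a change is that 9.2 is the only place where a success criterion is spelled out, and it is written as a decision (we will conclude), not as an illustration. No sentence gives the exact test precedence, and 9.3 does not print the 60% null. The evaluable number will often not be 33: under the binomial assumption at 5%, it is 32 or 33, the only values at which 25 is the exact cut-off, with probability just 0.43, and 34 or 35 with probability 0.47. A reader set on a bare count of 25 could then pass an arm that the test fails.

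Some of this stands. The sentence is clumsy, and the precedence is implied rather than written. But the criterion is a count out of 33 inside a sample-size section, while the analysis section names an exact test with no condition on the number evaluable. A design-stage cut-off followed by a named test is the usual structure, and the test governs. The null follows from two numbers in the same paragraph and reproduces the printed cut-off exactly, which leaves no real doubt about it. As for the wording on the combination, both arms receive telotristat with Lutathera, and 9.2 itself uses the word for what is tested in 33 patients per arm. The bracketed phrase therefore reads naturally as the regimen in whichever arm meets the criterion.

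**Conclusion.** The concern does not call for a change. No stated number is wrong: 25 of 33 is the correct exact cut-off against 60%, with size 4.4% and power 80.0%. No section contradicts another, because objective 1.1.1, 9.1 and 9.3 all put the test in each arm, and 9.2 fits them on the only reading that matches its own power and level. For a varying denominator, the test in 9.3 gives a defined answer at any evaluable number, and the proportion implied by 9.2 gives the same answer from 30 to 35. At the planned 5% non-evaluable rate the two differ for about 0.09% of arms at a true rate of 80%. The larger figures (7.3% and 11.2% size, 8% to 30% disagreement) depend on a reading that the text does not invite, and the 8.7% belongs to any pair of unadjusted per-arm tests.

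This rests on three assumptions: the null is 65% minus 5 points, the arms are independent, and non-evaluability is binomial. What is left is a loosely phrased sentence that a competent analyst resolves from the adjoining sections.
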